8.1 Definitions

Unanticipated Problems Involving Risk to Subjects or Others

Any incident, experience, or outcome that meets all of the following criteria:

- Unexpected in nature, severity, or frequency (i.e. not described in study-related documents such as the IRB-approved protocol or consent form, the investigators brochure, etc)

Version: 23, 7-25-17

- Related or possibly related to participation in the research (i.e. possibly related means there is a reasonable possibility that the incident experience, or outcome may have been caused by the procedures involved in the research)
- Suggests that the research places subjects or others at greater risk of harm (including physical, psychological, economic, or social harm).

Adverse Event

An **adverse event** (AE) is any symptom, sign, illness or experience that develops or worsens in severity during the course of the study. Intercurrent illnesses or injuries should be regarded as adverse events. Abnormal results of diagnostic procedures are considered to be adverse events if the abnormality:

- results in study withdrawal
- is associated with a serious adverse event
- is associated with clinical signs or symptoms
- leads to additional treatment or to further diagnostic tests
- is considered by the investigator to be of clinical significance

Serious Adverse Event

Adverse events are classified as serious or non-serious. A **serious adverse event** is any AE that fulfills at least one of the following criteria:

- is fatal
- is life-threatening
- requires or prolongs hospital stay
- results in persistent or significant disability or incapacity
- is a congenital anomaly or birth defect
- is an important medical event

Important medical events are those that may not be immediately life threatening, but are clearly of major clinical significance. They may jeopardize the subject, and may require intervention to prevent one of the other serious outcomes noted above. For example, drug overdose or abuse, a seizure that did not result in in-patient hospitalization, or intensive treatment of bronchospasm in an emergency department would typically be considered serious.

All adverse events that do not meet any of the criteria for serious should be regarded as **non-serious adverse events**.

Adverse Event Reporting Period

Adverse events must be reported once the subject undergoes any study procedures and adverse events must be reported during the entire active study period (6 weeks) and for 30 days following the last administration of study treatment.

General Physical Examination Findings

At screening, any clinically significant abnormality shall be recorded as a preexisting condition. Throughout the study, any new clinically significant findings/abnormalities that meet the definition of an adverse event must also be recorded and documented as an adverse event.

Post-study Adverse Event

All unresolved adverse events will be followed by the investigator until the events are resolved, the subject is lost to follow-up, or the adverse event is otherwise explained. At the last scheduled visit, the investigator will instruct each subject to report any subsequent event(s) that the subject,

Version: 23, 7-25-17

or the subject's personal physician, believes might be related to participation in this study. The investigator should notify the study sponsor and IRB of any serious adverse event or death occurring up to 30 days after the subject has discontinued or terminated study participation that may be related to this study. Study staff will contact the subject 30 days after study participation has ended to ask about possible adverse effects after study drug discontinuation.

Abnormal Laboratory Values

A clinical laboratory abnormality should be documented as an adverse event if any one of the following conditions is met:

- The laboratory abnormality is not otherwise refuted by a repeat test to confirm the abnormality
- The abnormality suggests a disease and/or organ toxicity (e.g. serum creatinine increases more than 0.4 mg/dL)
- The abnormality is of a degree that requires active management; e.g. change of dose, discontinuation of the drug, more frequent follow-up assessments, further diagnostic investigation, etc.

Hospitalization, Prolonged Hospitalization or Surgery

Any adverse event that results in hospitalization or prolonged hospitalization will be documented and reported as a serious adverse event unless specifically instructed otherwise in this protocol. Any condition responsible for surgery should be documented as an adverse event if the condition meets the criteria for an adverse event.

Neither the condition, hospitalization, prolonged hospitalization, nor surgery are reported as an adverse event in the following circumstance:

- Hospitalization or prolonged hospitalization for diagnostic or elective surgical procedures for a preexisting condition. Surgery should **not** be reported as an outcome of an adverse event if the purpose of the surgery was elective or diagnostic and the outcome was uneventful.

8.2 Recording of Adverse Events

At each contact with the subject, the investigator will seek information on adverse events by specific questioning and, as appropriate, by examination. Information on all adverse events will be recorded immediately in the source document (AE Assessment form), and also in the appropriate ongoing subject AE log. All clearly related signs, symptoms, and abnormal diagnostic procedures results will be recorded in the source document.

All adverse events occurring during the study period will be recorded. The clinical course of each event will be followed until resolution, stabilization, or until it has been determined that the study treatment or participation is not the cause. Serious adverse events that are still ongoing at the end of the study period will be followed up to determine the final outcome. Any serious adverse event that occurs up to 30 days after Visit 6 and is considered to be possibly related to the study treatment or study participation will be recorded and reported immediately.

8.3 Reporting of Serious Adverse Events and Unanticipated Problems

All serious adverse events (AE) will be reported to the appropriate authorities, including the UW IRB and DMC in the required timeframe. Adverse events and SAEs will be reported to the DMC and study sponsor (NHLBI) within the same time frame as required for the IRB (see 8.3.1 and 8.3.2 below).

Version: 23, 7-25-17

Investigators must conform to the adverse event reporting timelines, formats and requirements of the various entities to which they are responsible, but at a minimum those events that must be reported are those that are:

- related to study participation,
- unexpected, and
- serious or involve risks to subjects or others
- Multiple occurrences of an AE that, based on an aggregate analysis, is determined to be an unanticipated problem. There should be a determination that the series of AEs represents a signal that the AEs were not just isolated occurrences and involve risk to human subjects.
- An AE that is described or addressed in the investigator's brochure, protocol, or informed consent documents that occurs at a specificity or severity that is inconsistent with prior observations OR for which the rate of occurrence in the study represents a clinically significant increase in the expected rate of occurrence.
- Any AE or safety finding (e.g., based on animal or epidemiologic data) that would cause the sponsor to modify the investigator's brochure, study protocol, or informed consent documents, or would prompt other action by the IRB to ensure the protection of human subjects.

(see definitions, section 8.1).

If the report is supplied as a narrative, the minimum necessary information to be provided at the time of the initial report includes:

• Study identifier• Study Center• Subject number• A description of the event• Date of onset• Study AE Assessment form	
• Current status• Whether study treatment was discontinued• The reason why the event is classified as serious• Investigator assessment of the association between the event and study treatment
--	--

8.3.1 Investigator reporting: notifying the IRB

All adverse events and serious adverse events will be reported to the IRB at the appropriate and required time intervals. This will include acutely and yearly at the annual protocol renewal.

Will be reported immediately:

- Any serious adverse event that occurs any time during or up to 30 days after the research study, which in the opinion of the principal investigator meets all 3 of these criteria:
 1. Is Unexpected (An event is "unexpected" when its specificity and severity are not accurately reflected in the protocol-related documents, such as the IRB-approved research protocol, any applicable investigator brochure, and the current IRB-approved informed consent document and other relevant sources of information, such as product labeling and package inserts.)
 2. Is Related to the research procedures (An event is "related to the research procedures" if in the opinion of the principal investigator or sponsor, the event was more likely than not to be caused by the research procedures.)
 3. Is Immediately life-threatening or severely debilitating to other current subjects

Will be reported within 14 days:

- Any other adverse events listed below will be reported within 14 days

Version: 23, 7-25-17

1. A single occurrence of a serious, unexpected event that is uncommon and strongly associated with drug exposure (such as angioedema);
2. A single occurrence, or more often a small number of occurrences, of a serious, unexpected event not commonly associated with drug exposure, but uncommon in the study population.
3. Multiple occurrences of an AE that, based on an aggregate analysis, is determined to be an unanticipated problem. There should be a determination that the series of AEs represents a signal that the AEs were not just isolated occurrences and involve risk to human subjects (e.g. a comparison of rates across treatment groups reveals higher rate in the drug treatment arm versus a control).
4. An AE that is described or addressed in the protocol or informed consent documents that occurs at a specificity or severity that is inconsistent with prior observations OR for which the rate of occurrence in the study represents a clinically significant increase in the expected rate of occurrence.
5. Any AE or safety finding (e.g., based on animal or epidemiologic data) that would cause the sponsor to modify the investigator's brochure, study protocol, or informed consent documents, or would prompt other action by the IRB to ensure the protection of human subjects.

Will be reported annually at continuing progress review:

- Occurred locally (or at any WiNHR study sites);
- Are related to the research study but unexpected;
- Were not assessed as placing subjects or others at increased risks (including physical, psychological, economic, or social harm) than was previously known or recognized;
- Were not assessed as resulting in new information that needed to be disseminated to participants; and

8.3.2 Sponsor reporting:**Notifying NHLBI**

The investigators will appropriately notify NHLBI using expedited reporting to the NHLBI Program Officer for serious adverse events and unexpected problems. The reporting of adverse events and SAEs will be reported to NHLBI within the same timeframe as required by the IRB (see 8.3.1 above). Expedited safety reports will be sent concurrently to the DMC and NHLBI and the DMC response will be forwarded to NHLBI within 14 days.

8.3.3 Sponsor reporting: Notifying the FDA

The investigators will appropriately notify the FDA in safety reports. The following describes the safety reporting requirements by timeline for reporting and associated type of event:

- ***Within 7 calendar days***

Any study event that is:

- associated with the use of the study drug
- unexpected,
- fatal or life-threatening, and

- ***Within 15 calendar days***

Any study event that is:

- associated with the use of the study drug,

Version: 23, 7-25-17

- unexpected, and
- serious, but not fatal or life-threatening
- or-
- a previous adverse event that was not initially deemed reportable but is later found to fit the criteria for reporting (reporting within 15 calendar days from when event was deemed reportable).

8.4 Unblinding Procedures

Unblinding of the study medication will be done in emergent circumstances where the identity of the study medication needs to be known. All efforts will be made to maintain blinding except in the case of urgent medical necessity. If a subject needs to be unblinded, the study staff should contact the PIs and the PRC and the DMC for unblinding (using contact information below). The PI will work with the PRC to unblind the situation without compromising the blinding of remaining subjects. The investigator will follow all NIH and institutional rules for the timely and appropriate notification of the governing IRB. In most cases, the unblinding will be part of managing an SAE, and will be reported with the SAE, however, in cases where unblinding was not associated with an SAE, such actions should be reported in a timely manner.

Principal Investigators:

[name]: [contact] (office phone); [contact] (mobile)

[name]: [contact] (office phone)

Pharmaceutical Research Center (PRC): [contact]

Data Monitoring Committee (DMC): DMC contact [name] [contact]

8.5 Stopping Rules

In case there is a significant beneficial or harmful effect due to one or both of the treatment arms, which would require early termination of the study, we plan on having three interim data analyses. Interim analysis will be performed after approximately 33%, 66%, and 100% of the subjects complete the 6-week study period. Stopping criteria for benefit/harm will be based on the primary outcome variable analysis with O'Brien-Fleming alpha spending thresholds for three interim analyses. These thresholds are: $p=0.0005$ at look 1, $p=0.01413$ at look 2, and $p=0.04507$ at final analysis. The DMC, concurrent with and additional to the interim analyses, will meet on a quarterly basis to evaluate the protocol, subject accrual rates, subject retention, adverse events, and other aspects of the study. In those meetings which correspond to the times determined for interim analyses the DMC will also evaluate the benefit or harm of the treatments.

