Any deviations from the protocol at any of the research sites will be discouraged and if occur, will be reported to the UW HS IRB if the deviation or exception presents a significant safety risk to the subject or potential subject. As per Good Clinical Practices, protocol deviations will be documented and reviewed at the quarterly investigator meetings. If changes are necessary for the project, protocol modifications will be submitted to the HS IRB to change the protocol to fit the required changes.

6.5 *Unexpected Findings*

Whenever tests like the electrocardiogram (Visit 1), cardiac output (Visits 3 and 6), or serum laboratory tests are done, there is the chance of an unexpected finding. Subjects will be informed of all findings of clear clinical significance which may be revealed during the electrocardiogram, cardiac output procedure (limited echocardiography), and serum laboratory tests. Findings of clear clinical significance are those for which we generally know the risks of non-treatment and for which treatment may be available. If unexpected findings for the electrocardiogram, cardiac output, or serum laboratory tests are discovered, a letter describing the findings will be sent to the subject and to his/her physician with permission from the subject.

7 Statistical Plan

7.1 *Sample Size Determination*

The primary outcome will be the change in the slope response of MSNA during progressive hypoxia from baseline to 6 weeks. From previous data from our lab we have seen an approximate standard deviation for slope in OSA patients under similar progressive hypoxia of 8-10.

Based on interim data, a power calculation for the differences and standard deviations in primary outcome variable estimated that we would have 90% power (this is increased power from our original sample size calculation that used 80%) to determine a difference of 3.07 (1.13 vs -1.94) at a significance level of 0.017 (Bonferroni adjusted alpha for 3 tests) if we had complete MSNA slope response data from 20 subjects per group.

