We had originally proposed to enroll 50 subjects per group. Our interim analysis determined that if we obtain complete data in 20 subjects per group, we are likely to find a significant difference. We will enroll as many subjects as we can in the remaining time frame to give us the best possible chance at finding a difference. Consistent with DMC recommendations, we will reduce our sample size to 100 subjects. To account for drop-outs, we will ask to enroll 120 subjects to get 100 subjects who proceed to randomization.

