7.2 Statistical Methods

Data will be analyzed by a statistician blinded to drug assignment. Demographic comparisons to assess effectiveness of randomization will be examined between treatment arms by ANOVA and chi-square tests where appropriate. Differences in baseline values for all variables between treatment arms will be assessed using ANOVA. The paired differences in these same variables will be compared after the 6-week study period. These values include all measured physiologic variables, such as resting heart rate, blood pressure, plasma catecholamine concentrations, MSNA, cerebral blood flow, forearm blood flow, flow-mediated vasodilation, pulse wave velocity, augmentation index, polysomnographic measures, Pcrit, apnea threshold, and others.

The primary outcome variable is the difference in the individual slope of the MSNA – SaO₂ response curve at 6 weeks and baseline between treatment groups. The MSNA – SaO₂ response curve will be graphed with MSNA as the dependent variable and SaO₂ as the independent variable during progressive hypoxia. Slope response curves will also be calculated for heart rate, ventilation, forearm blood flow, cerebral blood flow, and blood pressure during hypoxia, hyperoxia and controlled breathing periods. MSNA will be expressed as burst frequency (bursts/min), burst amplitude (arbitrary units) and total minute activity (burst frequency x mean burst amplitude). MSNA will be averaged over the 5-min measurement periods at baseline, 90%, 85%, 80% hypoxia, and during controlled breathing. During hyperoxic trials, 15-sec averages of MSNA will be obtained, and an average of the 4 trials will be computed. The slope response of MSNA during progressive hypoxia will be calculated and will be analyzed using ANOVA. Changes in polysomnographic measures from baseline to the end of the 6-week treatment period between the treatment groups will be compared using ANOVA. If significant ANOVA p-values are found, then post-hoc multiple comparison Tukey HSD tests will examine differences between each arms. Multiple regression will be used to determine the influence of subject characteristics and hours of CPAP use on the primary outcome, and on the effect of treatment on the primary outcome.

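### Do the unlinked significance rules in sections 7.1, 7.2 and 8.5/8.6 leave the family-wise error uncontrolled?

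*Combined protocol and SAP*

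**What the plan says.** Three places in the combined protocol and SAP bear on significance for the primary outcome, the 6-week change in the MSNA–SaO₂ slope.

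- **7.1 Sample Size Determination** states power "to determine a difference of 3.07 (1.13 vs -1.94" units), "at a significance level of 0.017 (Bonferroni adjusted alpha for 3 tests"), with 20 complete subjects per group. It does not mention repeated looks. It also records the reduced size: "We had originally proposed to enroll 50 subjects per group", now 100 in total.
- **7.2 Statistical Methods** gives the analysis: "The slope response of MSNA during progressive hypoxia will be calculated and will be analyzed using ANOVA". If the ANOVA is significant, "then post-hoc multiple comparison Tukey HSD tests will examine differences between each arms". No alpha is given for either step.
- **8.5 Stopping Rules**, repeated in **8.6**, plans looks at about 33%, 66% and 100% of completers: "Stopping criteria for benefit/harm will be based on the primary outcome variable analysis", using O'Brien-Fleming levels. "These thresholds are: $p=0.0005$ at look 1, $p=0.01413$ at look 2, and $p=0.04507$ at final analysis". The purpose is to detect a "significant beneficial or harmful effect due to one or both of the treatment arms".

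No sentence links the three sections, and 8.5 does not name the p-value to be compared with its levels.

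**The concern.** The 8.5 levels are those of a single test sequence with a total of 0.05, while the trial has three arms and 7.1 divides alpha by three. If the DMC statistician applied the 8.5 levels to plain pairwise tests, nothing in 8.5 would correct for the number of arms, and the family-wise error would exceed 5%.

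If the levels apply to the ANOVA, the error is held, but an F test has no direction and names no arm. A boundary could then be crossed because losartan differs from allopurinol, with neither shown to differ from placebo, although the decision in 8.5 concerns benefit or harm of a treatment arm.

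The cut from 150 to 100 subjects also means that a look already held may sit at a different information fraction from the one printed.

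At stake would be a false claim at the final analysis or, less often, a mistaken early stop.

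**Working it through.** **Inputs.** Levels 0.0005/0.01413/0.04507 and looks at 33/66/100% (8.5); 0.017, difference 3.07, 90% power, 20 per group (7.1); ANOVA then Tukey (7.2); 100 randomised, originally 50 per group (7.1). Assumptions: equal allocation (about 33 per arm), two-sided tests, normal data.

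**1. Reproduce the 8.5 levels.** Classical O'Brien-Fleming for three looks: z_k = 2.004 × √(3/k), p_k = 2 × (1 − Φ(z_k)).

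| Look | z | p |
|---|---|---|
| 1 | 3.471 | 0.00052 |
| 2 | 2.454 | 0.01411 |
| 3 | 2.004 | 0.04507 |

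These match 8.5 to within rounding. The total crossing probability is 0.050, so the levels are correct for one test sequence at two-sided 0.05.

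**2. Compare 8.5 with 7.1.** Bonferroni: 0.05/3 = 0.0167, printed as 0.017. Tukey at 0.04507 with three groups of 20 has 60 − 3 = 57 df and a critical studentized range of 3.465. Dividing by √2 gives t = 2.450, a pairwise p of 0.0174. The final level in 8.5, applied through the Tukey step of 7.2, is therefore almost the level used for sizing in 7.1.

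**3. Family-wise error under no effect.** Simulation of 400,000 trials, looks at 11/22/33 per arm, pooled variance:

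| Reading | Any false positive |
|---|---|
| ANOVA at the 8.5 levels | 5.1% |
| Tukey p-values at the 8.5 levels | 5.1% |
| ANOVA, then Tukey, both at the 8.5 levels | 4.6% |
| ANOVA at the 8.5 levels at looks 1–2, ANOVA at 0.05 at the end | 5.5% |
| ANOVA at the 8.5 levels at looks 1–2, 0.017 per pair at the end | 5.0% |
| Unadjusted pairs at looks 1–2, 0.017 per pair at the end | 6.5% |
| Unadjusted pairs at looks 1–2, Tukey at 0.05 at the end | 7.0% |
| Two unadjusted drug–placebo pairs throughout | 9.1% |
| Three unadjusted pairs throughout | 12.2% |

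Looks at 7/13/20 or 17/33/50 per arm move these by about 0.1 percentage point. The first five rows use only tests that 7.1 or 7.2 describes. The last four need unadjusted pairwise tests at one or more looks; 7.1 adjusts its pairs by Bonferroni and 7.2 by Tukey. False early stopping is 1.4% on the ANOVA and stays below 4% even on three unadjusted pairs.

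**4. ANOVA crossings that do not implicate a drug against placebo.** In null trials, about 38% of ANOVA crossings have no Tukey-significant drug–placebo difference at that look. In absolute terms this is 0.38 × 5.1% = 1.9% of trials, and about 0.6% at looks 1 and 2 together. Losartan differing from allopurinol accounts for about 1.3% of trials; the rest have no significant pair at all.

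**5. Effect of the sample size cut.** If look 1 fell at 33% of 150, about 50 completers (an assumption), that is 50% of 100. The printed levels used at 50%, 66% and 100% spend about 5.0% in total, so the cut does not make them liberal.

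**6. Would two drug–placebo contrasts do better?** From 7.1, 90% power at 0.017 with 20 per group implies an SD of the change of about 2.55, so d = 3.07/2.55 ≈ 1.2. Final-look power is then 90.9% with ANOVA and Tukey at 0.04507, against 92.7% with a direct contrast at 0.0231 (20 per group); with 33 per group, 99.3% against 99.5%. At an illustrative d of 0.8 the gap is wider: 53% against 58%, and 79% against 83%.

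**The case for a change.** The best argument for a change is that 8.5 speaks of arms and of benefit or harm, and an F test delivers neither. Whoever applies the levels must choose a p-value, and that choice should be fixed before results are seen. A reader who takes 8.5 arm by arm could use plain pairwise tests and reach 9% to 12%. A written rule would cost little.

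Part of this stands. The p-value is not named, and 8.5 does not say that Tukey is run at the interim looks or at what level. But the phrase in 8.5 points to the analysis in 7.2, and its Tukey step supplies the pair and the direction. Because 8.5 asks for an effect attributable to a treatment arm, a DMC facing a significant F would look at the drug–placebo differences before acting. The case where it would matter arises in about 0.6% of null trials at the early looks.

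Replacing the ANOVA with two drug–placebo contrasts is a trade-off. It gains about 2 points of power at the effect in 7.1 (5 points at d = 0.8, 20 per group). It makes losartan versus allopurinol secondary, and it redefines the primary hypotheses after interim primary-outcome data were used to resize the trial.

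**Conclusion.** No change follows. The 8.5 levels reproduce and are right for one sequence at 0.05. Joined to 7.2 in the ordinary way, they hold the family-wise error at about 4.5% to 5.6%, and the final Tukey comparison (pairwise p 0.0174) agrees with the 0.017 in 7.1. Rates of 6.5% to 12% need unadjusted pairwise tests that no section describes. The gap is an unwritten cross-reference, which analysts would fill sensibly, in a phase II trial.

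This rests on equal arms, two-sided testing, normal data, and looks at or near the stated fractions. The power comparison also rests on the SD implied by 7.1. The interim SD of the change is not given, and the 8–10 quoted there is for the slope itself; taken as the SD of the change, it would give only 7% to 12% power. That affects the power figures but not the error rates, on which this conclusion depends.
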